### 1.3. Axitinib Molecular Formula and Molecular Activity

[figure not shown]
Axitinib, a substituted indazole derivative, is an oral, potent, and selective inhibitor of vascular endothelial growth factor (VEGF) receptors 1, 2, and 3.

**Figure 2: The molecular formula of Axitinib is  $C_{22}H_{18}N_4OS$ . It has a molecular weight of 386.47. The chemical name is N-Methyl-2-[3-((E)-2-pyridin-2-yl-vinyl)-1H-indazol-6-ylsulfanyl]-benzamide.**

Phase 2 studies with axitinib are ongoing or completed in various tumour types, including metastatic breast cancer (Protocol A4061010), non-small cell lung cancer (Protocol A4061011), cytokine-refractory renal cell carcinoma (RCC; Protocol A4061012, A4061035), radioiodine [ $^{131}I$ ]-refractory thyroid cancer (Protocol A4061014), malignant melanoma (Protocol A4061015), advanced pancreatic cancer (Protocol A4061016), colorectal cancer (CRC; Protocol A4061020, A4061034), sorafenib-refractory RCC (Protocol A4061023), iodine and doxorubicin-refractory thyroid cancer (Protocol A4061027), and non-small cell lung cancer (NSCLC; Protocol A4061030, A4061038, A4061039). A pivotal Phase 3 study in advanced pancreatic cancer (Protocol A4061028) was terminated early for futility.

Retrospective analyses of five AG-013736 Phase 2 studies across multiple tumour types (RCC, melanoma, NSCLC, and thyroid cancer) demonstrated that patients who developed at least one in-clinic measurement of dBP >90 mmHg at any point during treatment had significantly better clinical outcomes for OS (30.1 vs 10.2 months; hazard ratio [HR]=0.546;  $p<0.001$ ), PFS (13.1 vs 5.8 months; HR=0.42;  $p<0.001$ ), and ORR (43.9% vs 12.0 %;  $p<0.001$ ). Figure 2: below shows the association between transient dBP > 90 mmHg with longer median OS.

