#### **Secondary objectives of trial**

- To assess the correlation in patients with a confirmed vascular response (as evaluated by a greater than 20% reduction in CEPHI at 2 weeks).
  - This assessment will be done by separating out the RECIST-progressors (non-responders) who can also be detected by CEPHI at 2 weeks, and comparing this with RECIST responders (CR+PR+SD). The patients receiving Placebo will be included in this analysis.
  - To demonstrate the value of CEPHI as an early imaging selection biomarker of non-response (or response) in patients who have had at least 4 weeks of study treatment.
- To compare overall survival between the treatment and placebo arms
- To compare the overall RECIST response rate between the treatment and placebo arms
- To compare and correlate the 2 week CEPHI and 8 week RECIST response rates.
- To compare the median overall survival of patients receiving Axitinib who develop new diastolic hypertension (>90mmHg) with those that do not (in either/or the blinded placebo group or treatment group combined)
- To identify if CEPHI will function as a non-invasive correlative biomarker of Axitinib pharmacokinetics (PK) and help minimise toxicity and identify responders

CONFIDENTIAL

- Toxicity (CTC) i for the treatment and placebo arms

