### Secondary Endpoints

- To compare overall survival between the treatment and placebo arms
- To compare duration on study treatment between the treatment and placebo arms
- To compare the best overall RECIST response rate between the treatment and placebo arms
- To compare and correlate the 2-week CEHPI perfusion index and 8 week RECIST response rates in the ITT population
- To compare the median overall survival of patients receiving Axitinib who develop new diastolic hypertension ( $>90\text{mmHg}$ ) with those that do not (in either/or the blinded placebo group or treatment group combined)
- To identify if CEHPI will function as a correlative biomarker of Axitinib pharmacokinetics (PK) and help minimise toxicity and identify responders
- To compare toxicity (CTC) information for the treatment and placebo arms.
  - Type, incidence, severity, timing, seriousness of adverse events by Chemotherapy toxicity criteria (CTC) v4.03 grading.
- Axitinib PK analysis correlation with patients developing or not developing diastolic hypertension

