### 3. Study Design

A Phase II, double-blind, 2 arm pilot randomised placebo controlled trial. 50 patients will be sequentially randomised 2:1 to Axitinib or placebo.

Inclusion criteria: Chemorefractory third-line metastatic CRC with US-assessable liver or other abdominal metastases that can have a baseline DCEUS baseline measurement.

Treatment arm: Axitinib monotherapy started in all patients at 5mg bd, and increased fortnightly by a dose level (See Table 4) as tolerated to a maximum dose of 10mg bd.

Control arm: Placebo (blinded) randomised 2:1 to Axitinib : placebo

Follow up: Outpatient monitoring at 2 weeks and 4 weeks post first dose then 4 weekly thereafter with RECIST restaging every 8 weeks. CEHPI at baseline, 2 weeks and 8 weeks for assessment of differential blood supply (CEHPI) with an optional visit at 48-72 hours post first dose. VEGF-PK samples at Day 15 & Day 28 and at 8 weeks and RECIST progression. At 8 weeks, after tumour CT RECIST assessments, conventional responders (CR/PR/SD) continue monotherapy. In non-responders (PD), monotherapy can be continued if patient chooses to continue and if tolerated. CT response assessments continue at 8 weekly intervals in all patients, with parallel 8 weekly DCE-US. CEHPI at baseline, optionally at 47-72 hours, 2 weeks, 8 weeks and at progression of disease.

[figure not shown]

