## 5.11 Axitinib/Placebo Dose Reduction for Hypertension

Patients treated with Axitinib/placebo will be issued blood pressure cuffs (provided by Pfizer Inc) for home monitoring and instructed to measure their blood pressure (BP) twice daily, prior to taking each dose. All blood pressure measurements will be recorded in a diary and brought to the nurse or study coordinator at each clinic visit. Patients should be instructed by the study staff to contact their physician for guidance if their systolic blood pressure rises above 140 mm Hg, diastolic blood pressure rises above 90 mm Hg, or if they develop symptoms perceived to be related to elevated BP (eg, headache, visual disturbance). See below for dose modifications for hypertension. A different blood pressure threshold for contacting physician may be used according to the physician's clinical judgment. See below for dose modifications for hypertension.

New or additional antihypertensive therapy (see Section 5.4, Concomitant Medication(s) for guidance) should be started if 2 BP readings, preferably taken in the clinic and separated by at least 1 hour, show the following: 2 systolic BP readings greater than 140 or 2 dBP readings greater than 90 mm Hg. Alternately, the dose of existing antihypertensive medication(s) may be increased. Investigator may use clinical judgment to start new or additional antihypertensive therapy at a lower blood pressure threshold. If the patient is already on maximal antihypertensive treatment, the Axitinib dose should be reduced by 1 dose level (see Table 4).

Patients who have 2 systolic BP readings, separated by at least 1 hour, greater than 160 mm Hg, or 2 dBP readings, separated by at least 1 hour, greater than 105 mm Hg, will have treatment with Axitinib/placebo held. (Note: if Axitinib/placebo is held, patients receiving antihypertensive medications should monitor closely for hypotension and restart Axitinib/placebo at one lower dose level (see Table 4) as soon as BP is <140/90 mm Hg. The plasma half-life of Axitinib is 2 – 4 hours and BP usually decreases within 1-2 days following dose interruption.)

Patients removed from treatment for intolerable toxicity should still be followed with regular tumour assessments until disease progression or start of new treatment, and for survival thereafter.

Degree of Blood Pressure Elevation			
Systolic Pressure	OR	Diastolic Pressure	Management

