## **7.3 Blood Pressure Assessments**

Blood pressure readings should be taken in the seated position after the patient has been sitting quietly for 5 minutes and are required at each clinic visit. All patients receiving study drug will be issued a BP measurement diary. Blood pressure readings should be taken in the seated position after the patient has been sitting quietly for 5 minutes. Patients should be instructed to inform their doctor immediately if their systolic BP rises above 140 mm Hg, diastolic BP rises above 90 mm Hg, or if they develop symptoms perceived to be related to elevated BP (e.g. headache, visual disturbance). A different home blood pressure threshold for contacting physician may be used according to the physician's clinical judgment.

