## **7.9 Axitinib Pharmacokinetic Assessments**

No baseline pharmacokinetic testing is required as the value is known to be zero in those who have not received Axitinib.

On day 15 (day of CEHPI) medication will be taken after the ultrasound examination (time zero). After this blood samples will be taken at:

- 1 hour post dose
- 2 hours post dose
- 4 hours post dose

This will be repeated on day 28 and at restaging after 8 weeks at the usual clinic appointments. If there is disease progression pharmacokinetic testing will additionally be performed.

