### **7.9.1. Collection, Processing, Storage and Shipment of Pharmacokinetic Samples**

A 3 ml whole blood sample will be collected into K3-EDTA tubes to provide a minimum of 1 ml plasma for pharmacokinetic analysis and will be centrifuged (samples should be kept on ice or at 4°C until centrifugation), protected from light, at 1000 x g (at minimum) for 15 minutes at 4°C to separate the plasma. Plasma will be stored in appropriately labelled plastic amber cryovials at -20°C or lower until analysis. Plasma concentrations of Axitinib from patients on the active Axitinib treatment arm will be analysed using a validated analytical method in compliance with Pfizer standard operating procedures.

The following special precautions should be taken to minimize the rapid degradation of Axitinib in plasma when exposed to visible light:

- Following collection of blood samples, samples should be processed as soon as possible. Preferably, harvested plasma should be frozen within 1 hour of collection.
- Vacutainer tubes should be protected from light (covered completely in aluminium foil or in black protection tubes) while samples are waiting to be centrifuged to harvest plasma.
- Following centrifugation, plasma should be transferred rapidly to labelled plastic amber cryovials and stored at -20°C or lower.
- All samples should be transferred to an opaque box to protect from light exposure during storage and shipment. If a sample is inadvertently exposed to light (for 5 minutes or more), the sponsor should be notified so that the sample can be flagged for possibly spurious results.
- Once frozen, samples should not be allowed to thaw, including during shipment.
- Samples will be shipped with the completed sample inventory form and sufficient dry ice to last for at least two days.

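### The axitinib PK–blood pressure endpoint is defined only as a yes/no split and has no analysis method, although continuous diastolic readings are already recorded.

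*Combined protocol and SAP*

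**What the plan says.** Section 2.2 (Secondary Endpoints) lists "Axitinib PK analysis correlation with patients developing or not developing diastolic hypertension". The item gives no test, no time window and no pressure value. A figure appears in the neighbouring overall survival item, which compares patients "who develop new diastolic hypertension (>90mmHg) with those that do not". That cut matches the pooled retrospective analysis cited in section 1.3, which grouped "patients who developed at least one in-clinic measurement of dBP >90 mmHg at any point during treatment" and compared survival and response, not drug exposure.

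Section 9.3 describes PK against the ultrasound perfusion index only. Section 9.2 promises a similar analysis for diastolic pressure, but this follows the ROC paragraph on RECIST response and progression and does not mention PK.

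On the data available:
- Section 3: "50 patients will be sequentially randomised 2:1 to Axitinib or placebo".
- Section 7.9.1: "Plasma concentrations of Axitinib from patients on the active Axitinib treatment arm will be analysed".
- Section 7.9: "On day 15 (day of CEHPI) medication will be taken after the ultrasound examination (time zero"), followed by blood samples at 1, 2 and 4 hours, repeated at Day 28, week 8 and progression.
- Section 7.3: seated readings "are required at each clinic visit". The Schedule of Activities shows blood pressure at screening, pre-dose Day 1 and 2 weeks.
- Section 5.11: patients on study treatment measure twice daily at home. "All blood pressure measurements will be recorded in a diary and brought to the nurse or study coordinator at each clinic visit".

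**The concern.** A measured quantity is reduced to two groups before it is related to another measured quantity. If the 90 mmHg value is carried over from the survival item, a rise from 65 to 88 counts as no effect and a rise from 89 to 91 counts as an effect. The result then depends partly on where each patient started. Exclusion criterion 11 bars only uncontrolled pressure above 150/100, so some patients may enter with diastolic pressure already above 90. For them, developing hypertension is not defined.

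With at most about 33 patients contributing, a real exposure–pressure relation could easily be missed. Because no method is written down, the choice of test, PK summary and pressure reading would be made after the data are seen.

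**Working it through.** **No figure to reproduce.** The documents give no power, alpha, correlation or hypertension rate for this endpoint.

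**Inputs**
- n: 50 × 2/3 ≈ 33 (sections 3 and 7.9.1), before dropout or missed samples.
- Alpha: two-sided 5% (assumed; the one-sided 0.025 in section 9.2 applies to log-rank tests).
- Share above the cut, p: 30% and 44%, both assumed. The 44% is guided by 56/128 any-grade hypertension adverse events in the single-agent solid tumour column of the section 1.4 table, which is not the same as diastolic pressure above 90. The 30% has no source in the documents.
- Underlying correlation, r: 0.2 to 0.5 (assumed), with exposure and pressure bivariate normal.

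**Formulas**
- Continuous: power ≈ Φ(atanh(r)·√(n−3) − 1.96).
- Split: the same, with r replaced by r·φ(c)/√(p(1−p)), where c = Φ⁻¹(1−p).

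**Attenuation from the split**
- p = 0.30: c = 0.524, and 0.348/0.458 = 0.759. Relative efficiency is 0.759² = 0.58.
- p = 0.44: c = 0.151, and 0.394/0.496 = 0.795. Relative efficiency is 0.63.

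**Worked case, r = 0.4, √30 = 5.477**
- Continuous: 0.4236 × 5.477 − 1.96 = 0.36, power 64%.
- Split, p = 0.30: r becomes 0.304; 0.313 × 5.477 − 1.96 = −0.24, power 40%.
- Split, p = 0.44: r becomes 0.318; 0.329 × 5.477 − 1.96 = −0.16, power 44%.

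**Simulation (Pearson test against two-sample t-test, n = 33)**

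| r | Continuous | Split, p = 0.30 | Split, p = 0.44 | Gap, points |
|---|---|---|---|---|
| 0.2 | 20% | 13% | 14% | 6–7 |
| 0.3 | 40% | 25% | 27% | 13–15 |
| 0.4 | 65% | 41% | 45% | 20–24 |
| 0.5 | 86% | 61% | 66% | 20–25 |

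Smaller runs of 4,000 trials per cell spread the gap for r = 0.3 to 0.5 over 12 to 27 points, so about 12–27 allows for simulation error.

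**Sensitivity to antihypertensive treatment.** Suppose raw readings are used and every patient above the cut has pressure lowered by a fixed amount (r = 0.4–0.5, p = 30–44%):
- 1 SD lowering: continuous power 54–78% against 41–66% for the split. The gain shrinks to about 9–17 points.
- 1.5 SD lowering: continuous power 33–55%. It is now 3–18 points below the split.

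The advantage therefore belongs to readings taken before treatment changes, not to continuous readings of any kind.

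**The case against.** The strongest case for the split has four parts.

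1. The cut is not arbitrary here. Section 1.3 links it to outcome and a companion endpoint compares survival on it, so asking whether exposure differs between the same groups is coherent. This stands, and is why the split should be kept as support.

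2. A patient classed as ever hypertensive stays so classed after treatment, whereas later continuous readings fall. The text of section 5.11 calls for new or additional antihypertensives after two diastolic readings above 90. (Table 6 gives a different threshold; the two need reconciling.) This stands against raw readings, and the sensitivity check shows it can reverse the gain. It is met by a rule that takes the last reading before the change, though that reading is then earlier than the Day 15 concentration.

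3. The power comparison splits and correlates the same variable, whereas a Day 15 analysis drops later samples and later-onset hypertension. Under section 5.8, upward titration needs two tolerated weeks. Day 15 thus largely avoids pressure-driven dose changes but may narrow the exposure range. If the correlation fell by 0.1 as a result, the gain would roughly vanish: 65% continuous at 0.4 against 61–66% split at 0.5. A mismatch also runs the other way. Crossing a fixed level depends on baseline as well as change. If baseline and change were independent with equal SDs (assumed), r = 0.4 with change would become 0.4/√2 = 0.28 with level, and split power would be only about 22–24%.

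4. Section 9.1 says the sample does not allow conventional powering for OS, PFS or response rate. That limits the consequence, but is no reason to discard information.

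A reader might also infer that the plan commits to analysing PK only by a 90 mmHg split. It does not: the PK item states no value, and section 9 states no PK–pressure analysis at all.

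**Conclusion.** The point holds in this form: the endpoint is defined only as a yes/no grouping, no method is given for it, and a more informative measurement is already in the record. At n = 33, two-sided 5%, r = 0.3–0.5 and 30–44% above the cut, the split costs about 12–27 points of power, and about 6–7 at r = 0.2.

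That range should not be read as a property of this trial. The documents supply neither the correlation nor the share above the cut. The figures also assume bivariate normality, no missing PK and no reading lowered by antihypertensives.

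The primary analysis and the go-forward decision are unaffected. It is worth correcting because text for this endpoint must be written in any case.

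**What to change.** Add to section 9.3:
- **Main analysis.** Correlation and regression slope, each with 95% CI, of one prespecified log exposure summary from the Day 15 samples at 1, 2 and 4 hours (for example the log of partial AUC) against change in seated clinic diastolic pressure from pre-dose Day 1 to Day 15.
- **Antihypertensives started or increased before Day 15.** Use the last reading before that change. The only scheduled clinic reading in between is the optional 48–72 hour visit, so the rule should say which on-treatment reading counts (an unscheduled clinic reading, otherwise the diary) and never default to the pre-dose value. Report how many patients this affects.
- **Sensitivity analysis.** On-treatment home-diary means. A home-based change from baseline is not available, because no pre-treatment diary is described.
- **Supportive comparison.** Keep the >90 mmHg split, to match the survival endpoint and capture later-onset hypertension. State the value in the PK item, and say how patients already above it at baseline are counted.

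The cost is SAP wording, plus diary data entry for the sensitivity analysis; no new visit, sample or patient is needed. The downsides are small: the antihypertensive rule must be written, and the Day 15 anchor leaves later-onset hypertension to the supportive split.

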### 3. Study Design

A Phase II, double-blind, 2 arm pilot randomised placebo controlled trial. 50 patients will be sequentially randomised 2:1 to Axitinib or placebo.

Inclusion criteria: Chemorefractory third-line metastatic CRC with US-assessable liver or other abdominal metastases that can have a baseline DCEUS baseline measurement.

Treatment arm: Axitinib monotherapy started in all patients at 5mg bd, and increased fortnightly by a dose level (See Table 4) as tolerated to a maximum dose of 10mg bd.

Control arm: Placebo (blinded) randomised 2:1 to Axitinib : placebo

Follow up: Outpatient monitoring at 2 weeks and 4 weeks post first dose then 4 weekly thereafter with RECIST restaging every 8 weeks. CEHPI at baseline, 2 weeks and 8 weeks for assessment of differential blood supply (CEHPI) with an optional visit at 48-72 hours post first dose. VEGF-PK samples at Day 15 & Day 28 and at 8 weeks and RECIST progression. At 8 weeks, after tumour CT RECIST assessments, conventional responders (CR/PR/SD) continue monotherapy. In non-responders (PD), monotherapy can be continued if patient chooses to continue and if tolerated. CT response assessments continue at 8 weekly intervals in all patients, with parallel 8 weekly DCE-US. CEHPI at baseline, optionally at 47-72 hours, 2 weeks, 8 weeks and at progression of disease.

[figure not shown]
#### Trial Treatment

Axitinib or placebo will be administered, twice daily (bd) on a continuous daily dosing schedule, to patients randomised to Arm A or Arm B, respectively. The starting dose will be 5mg BD which will be increased fortnightly by a dose level (See Table 4) as tolerated to a maximum dose of 10mg bd. Doses should be taken with food as close to 12 hours apart as possible and at approximately the same times each day on a continuous schedule. Patients who tolerate Axitinib/placebo with no adverse events related to Axitinib/placebo above CTCAE Grade 2 for a consecutive 2-week period should have their dose increased by one dose level unless BP is >150/90 mm Hg. [The clinical judgment of the treating physician should be exercised when titrating Axitinib/placebo dose. In cases where it is not obvious whether Axitinib is a contributor to adverse event(s), dose titration will remain at the investigator's discretion.

The study treatment may be permanently discontinued upon progression of disease, occurrence of unacceptable toxicity, withdrawal of patient consent, or other withdrawal criterion is met. However, patients who have progressive disease (PD) but have experienced clinical benefit from Axitinib or placebo treatment will be eligible for continued treatment

provided that the treating physician has assessed the risk/benefit of taking such an approach and no alternative treatment is available.

Patients who require different systemic cancer treatment from what they were assigned at randomization must be withdrawn from the study and followed as described below. After discontinuation of study treatment and the mandated 28-day follow-up period, patients will continue to be followed in order to collect information on further anti-tumour therapy and survival.

## 4. Subject Selection

### 4.1. Inclusion criteria

Patients must meet all of the following inclusion criteria for enrolment:

1. Histologically or cytologically confirmed adenocarcinoma of the colon or rectum with liver metastas(es) or other measurable lesion. At least one of which should not have had any focal therapy including radiofrequency ablation.
2. Evidence of uni-dimensionally measurable disease as defined by the Response Evaluation Criteria in Solid Tumours (RECIST).
3. 18 years of age or older.
4. ECOG performance status of 0 or 1.
5. Failed (or intolerant of ) at least 2 chemotherapy regimens in advanced disease and resolution of any acute toxic effects of prior therapy e.g. radiotherapy or surgical procedure to NCI CTCv4 grade  $\leq 1$ . No other alternative available effective treatment options.
6. Adequate organ function as defined by the following criteria:
7. Serum aspartate aminotransferase (AST; serum glutamic oxaloacetic transaminase [SGOT]) and serum alanine aminotransferase (ALT; serum glutamic pyruvic transaminase [SGPT])  $\leq 5$  x upper limit of normal (ULN).
8. Total serum bilirubin  $< 1.5$  x ULN
9. Serum albumin  $\geq 25$ mg/dl
10. Absolute neutrophil count  $\geq 1500/\mu\text{L}$
11. Platelets  $\geq 75,000/\mu\text{L}$
12. Haemoglobin  $\geq 9.0$  g/dL
13. Serum creatinine  $\leq 1.5$  x ULN
14. Signed and dated informed consent form
15. Willingness and ability to comply with scheduled visits, treatment plans, laboratory tests, and other study procedures

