Mild hepatic impairment did not alter Axitinib plasma exposures ( $AUC_{0-\infty}$  and  $C_{max}$ ) compared to normal hepatic function. However, there was a ~2-fold increase in axitinib  $AUC_{0-\infty}$  and a 1.3-fold increase in Axitinib  $C_{max}$  in subjects with moderate hepatic impairment compared to subjects with normal hepatic function (see below).

Treatment Group	$C_{max}$ (ng/mL)		$AUC_{0-\infty}$ (ng.hr/ml)	
	Mean a	Ratio b (90% CI)	Mean a	Ratio b (90% CI)
Normal Hepatic Function; n=8	30.4	---	156	---
Mild Hepatic Impairment; n=8	27.0	0.89 (0.49-1.60)	122	0.78 (0.40-1.54)
Moderate Hepatic Impairment; n=8	38.9	1.28 (0.71-2.30)	304	1.95 (1.00-3.83)

**Table 3: Hepatic Impairment Study A4061035: Summary of Statistical Analysis of Axitinib Plasma Pharmacokinetics ( $AUC_{0-\infty}$  and  $C_{max}$ ).**

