Axitinib metabolism may be induced in patients taking potent CYP3A4/5 or CYP1A2 inducers (carbamazepine, dexamethasone, felbamate, omeprazole, phenobarbital, amobarbital, phenytoin, primidone, rifabutin, rifampin, nevirapine, and St John's wort) and this may reduce Axitinib plasma concentrations. Patients who require concomitant treatment with potent CYP3A4/5 or CYP1A2 inducers are not eligible for the study. Since CYP1A2 is also known to be induced in chronic smokers, there is likelihood that Axitinib plasma concentrations may be reduced in these individuals. (Note: these patients are not excluded from enrolment, however.)

The ability of Axitinib to increase concentrations of co-administered drugs was also investigated in studies with human liver microsomes. At expected therapeutic plasma concentrations (0.01 to 1.0 µg/mL), Axitinib appears most likely to inhibit the drug metabolizing enzymes CYP1A2 and CYP2C8, 2 enzymes not frequently observed as predominant drug metabolizing enzymes. Theophylline and tacrine are among the few drugs whose plasma concentrations are likely to be increased by Axitinib.

Axitinib is highly bound to proteins in human plasma (99.0% bound at concentrations between 0.2-20 µg/mL). Therefore, drug interactions with other agents that are also highly bound to plasma proteins are a possibility.

Patients who need to be on chronic antacid therapy with histamine H2 antagonists (e.g., cimetidine [Tagamet®], famotidine [Pepcid®], nizatidine [Axid®], ranitidine [Zantac®]), proton-pump inhibitors (eg, lansoprazole [Prevacid®], rabeprazole [Aciphex®], pantoprazole [Protonix®], and esomeprazole [Nexium®]), or locally acting antacids (eg, Maalox®, Milk of Magnesia®, Amphojel®) should stagger the timing of their Axitinib and antacid dosing. Patients should avoid use of antacids for 2 hours before through 2 hours after taking Axitinib/placebo tablets. Note, however, that patients taking the proton-pump inhibitor omeprazole (Prilosec®) are not eligible for this study and that patients should not use omeprazole while taking Axitinib/placebo tablets because omeprazole is a CYP1A2 inducer.

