## Appendix 1 Required laboratory tests

Laboratory Test	Conventional Units	Conversion Factor	SI Units
Hematology			
hemoglobin (Hgb)	g/dL	x 10	µg/L
platelet count (Plt)	10  /mm 	x 10 	10  /L
white blood count (WBC)	10  /mm 	x 10 	10  /L
white blood cell differential	%	x 0.01	fraction
Chemistry			
total bilirubin	mg/dL	x 17.1	mmol/L
alanine transaminase (ALT)	U/L	N/A	U/L
aspartate transaminase (AST)	U/L	N/A	U/L
alkaline phosphatase	U/L	N/A	U/L
gamma-glutamyl-transpeptidase (GGT)	U/L	N/A	U/L
lactate dehydrogenase (LDH)	U/L	x 0.016667	µkat/L
total protein	g/dL	x 10	g/L
albumin	g/dL	x 10	g/L
sodium	mEq/L	x 1.0	mmol/L
chloride	MEq/L	x 1.0	mmol/L
potassium	mEq/L	x 1.0	mmol/L
calcium	mg/dL	x 0.25	mmol/L
phosphate	mg/dL	x 0.323	mmol/L
blood urea nitrogen (BUN)	mg/dL	x 0.357	mmol/L
creatinine	mg/dL	x 88.4	µmol/L
glucose	mg/dL	x 0.055	mmol/L
TSH	µU/mL		
free T3	pg/dL		
free T4	pg/dL		
Hepatocellular carcinoma tumor marker			
α-Fetoprotein	ng/mL	x 1.0	µg/L
HBV panel, HCV antibodies			
HBsAg, HBe and anti-HBc	N/A		
Anti-HCV antibodies	N/A		
Coagulation			
Prothrombin Time (or INR)	secs (or NA)	N/A	secs (or NA)
Urinalysis			
Urine protein, glucose, blood	N/A	N/A	N/A

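### The albumin entry limit in inclusion criterion 9 is written in mg/dl, which puts it at 0.25 g/L; applied literally, the criterion excludes nobody

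*Combined protocol and SAP*

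**What the plan says.** Section 4.1 requires patients to meet every inclusion criterion. Criterion 6 introduces a group of laboratory limits with the words "Adequate organ function as defined by the following criteria", and criteria 7 to 13 supply them. Criterion 9 is the albumin limit: "Serum albumin $\geq 25$ mg/dl". The haemoglobin limit in the same group is also a mass concentration, and it is given in a different unit: "Haemoglobin $\geq 9.0$ g/dL".

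Appendix 1 lists the required laboratory tests with conventional units, conversion factors and SI units. Its albumin row reads "albumin g/dL x 10 g/L". Section 7.6 names albumin among the chemistry tests without a unit, and section 6.1 asks for chemistry within 7 days of the start of treatment. No other section gives an albumin limit for entry, and none corrects the unit in criterion 9.

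**The concern.** Criterion 9 is a binding threshold for entry, not background text. The unit it uses for albumin appears nowhere else in the protocol for that test, and it places the limit far below either unit in Appendix 1. If the criterion cannot exclude anyone, one of the seven limits that define adequate organ function has no effect. If staff recognise the slip and read another unit, enrolment follows a threshold that is not written down, and a monitor checking compliance cannot say from the protocol whether a given patient met criterion 9.

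**Working it through.** This is a unit conversion. The plan derives no figure (sample size, power or number of events) from this criterion, so there is none to reproduce.

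**Inputs**
- Limit as written: 25 mg/dl (section 4.1, criterion 9).
- Units used for albumin: g/dL, times 10 to give g/L (Appendix 1, albumin row).
- Range of patient values: not given in the documents. Assumed here as 10 to 35 g/L, where 10 g/L stands for a severely low value.

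**Step 1. Put the written limit on the Appendix 1 scale.**
- 25 mg/dL ÷ 1000 = 0.025 g/dL
- 0.025 g/dL × 10 = 0.25 g/L

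**Step 2. Compare assumed patient values with the limit** (1 g/L = 100 mg/dL).

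| Albumin, g/L (assumed) | In mg/dL | Multiple of the written limit (÷ 25) |
|---|---|---|
| 10 | 1000 | 40 |
| 15 | 1500 | 60 |
| 20 | 2000 | 80 |
| 25 | 2500 | 100 |
| 35 | 3500 | 140 |

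Even the lowest assumed value clears the limit 40-fold.

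**Step 3. Try the number 25 in each Appendix 1 unit.**
- As g/L: 25 g/L = 2.5 g/dL = 2500 mg/dL. Ratio to the written limit: 25 ÷ 0.25 = 100.
- As g/dL: 25 × 10 = 250 g/L, which is 250 ÷ 35 = about 7 times the top of the assumed range, so every patient in that range would fail.

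Of the three readings, mg/dl admits everyone in the assumed range and g/dL admits no one. Only g/L gives a limit that can separate patients. That makes g/L the likely intention, but the documents do not say so.

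**The case against.** The strongest reply is that the practical effect is small. The literal limit is so implausible that a clinician would probably see a unit slip and not apply it. Recruitment is from the oncology clinics of one trust (section 5.1), which limits divergent readings. Other screening remains: AST and ALT up to 5 × ULN, bilirubin below 1.5 × ULN and ECOG 0 or 1 (section 4.1); underlying coagulopathy as an exclusion (section 4.2, no. 8); APTT and INR at screening (section 6.1); and exclusion 17, which lets the investigator refuse a patient whose laboratory abnormality adds excess risk. Appendix 1 is not a clean reference either: its haemoglobin row converts g/dL to µg/L with a factor of 10.

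All of this stands, and it lowers the likely harm. It does not make the written criterion correct. None of these safeguards is a numeric albumin limit, and the albumin row of Appendix 1 is dimensionally right whatever the faults of other rows.

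A reader might also infer stronger consequences. The documents do not support them:
- *Exposure, safety or early failure.* Section 5.17 says "Axitinib is highly bound to proteins in human plasma", but it does not name albumin and raises only drug interactions. Section 1.4 reports that "there was a ~2-fold increase in axitinib" AUC with moderate hepatic impairment, but by Child-Pugh class in groups of 8, with no link to albumin. No section ties low albumin at entry to early failure.
- *How many patients would be affected.* Table 2 shows hypoalbuminaemia in 162/343 (47%), with Grade 2 or worse in (39 + 6)/343 = 13%. These are maximum grades in treated patients, not screening values, and the table gives no g/L cut-offs. They cannot show how many candidates for this trial would fall below any entry limit.
- *A programmed check that passes everyone.* The documents describe a central randomisation system and an electronic CRF database. They describe no automated eligibility check.

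**Conclusion.** Criterion 9 is wrong as written. It sets the albumin limit at 0.25 g/L, and over the assumed range of 10 to 35 g/L no patient can fail it. That conclusion needs only that assumption, and it would hold over any plausible range. The 100-fold figure is conditional: it is exact if the number 25 was meant in g/L, which is inferred from the number and the Appendix 1 units. The extracted text is explicit and does not look like a reading fault, although this cannot be fully excluded without the source page.

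The point is limited to one entry criterion. It does not show that unsuitable patients would be enrolled, or that hepatic screening as a whole is lost. No endpoint definition, sample size or analysis depends on it.

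**What to change.** Reconcile criterion 9 in section 4.1 with the albumin row of Appendix 1. The sponsor should confirm the intended limit and state value and unit together. An instruction to use the Appendix 1 unit is not enough, because that row gives two, and changing mg/dl to g/dL while keeping the number gives 250 g/L. No value is proposed here. The same unit should appear on the CRF page that records eligibility.

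The cost is one line in the protocol and a matching label on the CRF. If patients have already been screened, the limit actually used should be documented, so that compliance with criterion 9 can be verified.
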